Sonothrombolysis in Patients with an ST-segment Elevation Myocardial Infarction Protocol #ST2017-Pro00067953 Version (3): 13-Feb-2017 amount of the ultrasound contrast agent Definity® will be similar to what is clinically used in stress echocardiography and not exceed the maximum dose which is approved for clinical use.

Immediately after the diagnostic ultrasound, the therapeutic ultrasound will start using the same transducer by applying multiple high mechanical index (MI) ultrasound impulses (HMI). The HMI are the same as those which are used for assessment of myocardial perfusion in diagnostic ultrasound. These pulses will be applied in the apical 4-, 2-, and 3-chamber views to the apical windows that contained the risk area. The intervals between HMI impulses will vary from 5 to 15 s depending on the time required for myocardial contrast replenishment.

The following measurements will be performed on the recordings obtained before sonothrombolysis, after completion of sonothrombolysis, 72h or prior to hospital discharge and 3 months after sonothrombolysis:

- 1. Wall motion score index (WMSI) will be computed by analyzing wall thickening in all 3 contrast-enhanced apical windows using a 17-segment model as recommended in the 2015 American Society of Echocardiography Recommendations for Chamber Quantification.
- 2. Biplane measurements of LVEF by the the Simpson method
- 3. Microvascular perfusion score index (MPSI) within the same 17-segment model used for assessment of regional wall motion using a scoring system of 1 for myocardial contrast replenishment within 4 s of the applied HMI impulse; a score of 2 (mildly reduced) when complete replenishment within the risk area is delayed longer than 4 s after the HMI impulse; or a score of 3, which was defined as virtually no replenishment of myocardial contrast over 10 s after the MI impulse. The score index will be computed as total score divided by total number of segments analyzed. Attenuated basal segments will not be included in the calculation.
- 4. Global longitudinal strain

Table.1 Diagnostic and therapeutic procedures

Baseline diagnosis of STEMI (pre-reperfusion)		
day 1	12-lead electrocardiogram-baseline	in ER
day 1	Diagnostic Ultrasound - baseline	start in ER or cath lab
		Myocardial Contrast Echo (MCE)
		LV ejection fraction
		WMSI
		Global longitudinal strain
day 1	Sonothrombolys is A	start immediately after MCE
		prior to reperfusion

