7.2 Secondary Outcomes

- 1. Complete ST-segment resolution (≥50%) at 30 minutes post PCI as assessed by the worst lead on electrocardiogram
- 2. Left ventricular function as assessed by left ventricular ejection fraction (LVEF) by echocardiography (ECHO) (Simpson method) assessed on day 1 (pre and post reperfusion), day 3±2 (discharge) and 90±2 days after infarction.
- 3. Left ventricular function as assessed by wall motion score index (WMSI) by ECHO assessed on day 1 (pre and post reperfusion), day 3±2 (discharge) and 90±2 days after infarction.
- 4. Left ventricular function as assessed by microvascular perfusion score index (MPSI) by ECHO assessed on day 1 (pre and post reperfusion), day 3±2 (discharge) and 90±2 days after infarction.
- 5. Left ventricular function as assessed by global longitudinal strain by ECHO assessed on day 1 (pre and post reperfusion), day 3±2 (discharge) and 90±2 days after infarction.

7.3 Safety Outcomes:

- 1. Allergic reaction to Definity®
- 2. Vasospasm in culprit coronary artery
- 3. Adverse events (see appendix)

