8. DEFINITIONS OF STUDY OUTCOMES

8. 1 ST-segment Resolution

ECGs will be evaluated centrally at the ECG core laboratories (Canadian VIGOUR Centre, Edmonton, Canada) without knowledge of treatment, procedural results, or clinical outcomes. ST-E will be measured at the J point with magnified calipers to the nearest 0.05 mV. ST-E sums (ST-E) will be calculated as follows: for anterior infarction, the sum of ST-E in V1 to V6, I, and aVL; for inferior infarction, the sum of ST-E in leads II, III, aVF, V5, and V6. ST-segment depression will also be measured at the J point by similar methods. ST-segment deviation sums (ST-D) will be calculated by adding the sum of ST-segment depression measured in reciprocal leads to _ST-E. Leads II, III, and aVF will be considered potential reciprocal leads for inferior infarctions, and leads V1 through V4 will be considered potential reciprocal leads for inferior infarctions.

The resolution of ST-segment elevation (worst lead) prior to PCI and at 30 minutes post PCI will be classified according to the number of patients achieving complete ST-segment resolution (>50%) versus no ST-segment resolution (≤50%). The resolution of ST-segment elevation (worst lead) at discharge will be calculated using the discharge ECG using the above criteria.

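### The echo secondary outcomes have no masked reading, so reader expectation can enter them, chiefly the visual segment scores WMSI and MPSI

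*Combined protocol and SAP*

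**What the plan says.** **ECG.** Section 8.1 states that "ECGs will be evaluated centrally at the ECG core laboratories", and that this is done "without knowledge of treatment, procedural results, or clinical outcomes".

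**Echo.** Section 5.2 says: "The following measurements will be performed on the recordings obtained before sonothrombolysis, after completion of sonothrombolysis"; recordings at 72 hours or before discharge, and at three months, follow. It lists four readings: WMSI, biplane LVEF, MPSI and global longitudinal strain. MPSI grades each segment from 1 to 3 by how quickly contrast returns. The index is the summed score divided by the number of segments analysed, and basal segments lost to attenuation drop out.

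Section 7.2 makes these readings secondary outcomes 2 to 5. For example, outcome 3 is "Left ventricular function as assessed by wall motion score index (WMSI) by ECHO assessed on day 1 (pre and post reperfusion" and outcome 4 is "Left ventricular function as assessed by microvascular perfusion score index (MPSI) by ECHO assessed on day 1 (pre and post reperfusion", each with later scans at discharge and about 90 days. (The synopsis and section 1.0 omit strain, so this numbering follows section 7.2.)

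Section 8.2.3 builds a reperfusion definition on segment scores of 1 or 2 in the infarct territory and/or later recovery of systolic function.

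Section 9 repeats the scanner, transducer and views. It gives no reader and no analysis for the echo outcomes. Section 12 says only that a sonographer or fellow on call performs the imaging.

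**The concern.** WMSI and MPSI are judged by eye, segment by segment. As written, the plan allows the person who scanned and treated the patient to score the loops while knowing which scan is pre-treatment, which is post-treatment, and what the angiogram showed. Someone who expects improvement may resolve borderline segments in that direction on the later scans. Such a shift runs the same way across patients, so averaging does not remove it.

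There is no control arm, so the serial scans are the study's only internal echo comparison. The secondary and tertiary objectives (4.2, 4.3) instead set the results against published results of standard care. Optimistic scoring of post-treatment scans would distort that comparison too. Section 18 expects the study to lead to a randomized trial aimed at microvascular function, the property MPSI is meant to describe.

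**Working it through.** The plan states no figure on this point, so there is nothing to reproduce. The check is a comparison of the text, followed by arithmetic on the index.

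**1. What is specified for each reading**

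| | ECG (8.1) | Echo (5.2, 7.2, 8.2.3, 9, 12) |
|---|---|---|
| Who reads | Core laboratory | Not stated |
| Masked to treatment | Yes (little value in one arm) | Not stated |
| Masked to procedural result | Yes | Not stated |
| Masked to clinical outcome | Yes | Not stated |
| Masked to time point | Not stated | Not stated |
| Reading order | Not stated | Not stated |

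**2. How many readings.** 15 patients (section 6) × 4 recordings (section 5.2) = 60 studies.

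**3. Sensitivity of the index.** If *k* segments are each scored one grade differently and *m* segments are analysed, the index moves by *k*/*m*. The protocol gives this summed-score form for MPSI; I assume the same form for WMSI. The values of *k*, and *m* = 14 and 11, are assumptions. Only *m* = 17 is the protocol's full model.

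| *k* | *m* = 17 | *m* = 14 | *m* = 11 |
|---|---|---|---|
| 1 | 1/17 = 0.059 | 0.071 | 0.091 |
| 2 | 2/17 = 0.118 | 0.143 | 0.182 |
| 3 | 3/17 = 0.176 | 0.214 | 0.273 |

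If the shift affects a later scan but not baseline, all of it appears in that patient's change. If it occurs in every patient, the mean change moves by the same amount. If it occurs in 5 of 15 (also assumed), a two-segment shift moves the mean by 0.118 × 5/15 = 0.039.

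**4. Effect at n = 15.** The plan gives no test and no standard deviation for these outcomes. Assume a paired t-test at two-sided 0.05, no true change, and a reader shift of δ standard deviations of the change. The chance of a false improvement in one outcome is P(T > t₀.₉₇₅,₁₄), where T is noncentral t with 14 degrees of freedom and noncentrality δ√15.

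| δ | 0 | 0.1 | 0.2 | 0.3 | 0.5 |
|---|---|---|---|---|---|
| False improvement | 2.5% | 5.5% | 10.8% | 19.0% | 43.8% |

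The documents do not say where in this range the study would fall.

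**5. The threshold in 8.2.3.** If the definition requires every infarct segment to score 1 or 2, regrading a single segment from 3 to 2 can change a patient's classification.

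**The case against.** **The plan is silent; it does not say reading is unmasked.** That is correct, and the investigators may intend masked reading. But the plan as written does not require it.

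**The written question is not change over time.** Objectives 4.2 and 4.3 compare with reported standard therapy. Within-patient change is an inference from the serial schedule and from 8.2.3. Shuffling time points helps the external comparison less, since the reader still knows every patient was treated. It does stop leniency from being aimed at post-treatment scans in particular.

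**Masking would not identify the treatment effect.** This stands. PPCI takes place between the first and second scans (Table 1), so even perfectly masked readings mix sonothrombolysis with PPCI and natural recovery.

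**The outcomes are not equally exposed.** LVEF by the Simpson method and strain are measurements. MPSI has cut-offs at 4 s and 10 s that narrow, but do not remove, discretion. Leaving out attenuated segments is a further reader decision.

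**ECG is an imperfect model.** Its masking does not mention time point either, so the contrast is smaller than it first looks.

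**No stated decision rests on echo.** The synopsis ties progression to patency above 60%, and the primary outcome uses ECG and TIMI flow. Nor is echo the only evidence on perfusion, since section 9 also uses ST resolution 30 minutes after PCI.

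These points narrow the finding. They do not supply the missing masking provision.

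**Conclusion.** The plan masks ECG reading to treatment, procedural results and clinical outcomes, but masks no echo reading to anything. Reader expectation can therefore enter secondary outcomes 2 to 5 of section 7.2: mainly WMSI, MPSI and the 8.2.3 definition, and less so LVEF and strain. The size is unknown. The 0.06 to 0.18 index shift assumes one to three segments moved by one grade with all 17 analysed; it is an illustration, not an estimate.

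A reader might infer that bias is certain, that it affects all four outcomes alike, or that masked reading would let the echo changes be credited to sonothrombolysis. The documents support none of these: they give no data on reader behaviour, the four measures differ in kind, and PPCI lies between the scans. The primary outcome and the 60% patency rule are unaffected. The change is worth making because it removes an avoidable source of error cheaply, but the study does not stand or fall on it.

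**What to change.** Add to sections 5.2 and 9:

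- The research reading of WMSI, MPSI, LVEF and strain is made from the stored loops, de-identified and in random order across patients and time points, with date, time point, ECG and TIMI result removed.
- Reading is done in batches after the 90-day scans.
- The reader is a named role in the existing study team, preferably someone who did not perform that patient's scan or treatment.
- The 8.2.3 classification is derived from these masked readings and not judged afresh.

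The cost is de-identifying and shuffling about 60 studies, with research readings available later. No extra scan, visit or reader is needed, and any reading made at the bedside during treatment is untouched. Some time points may still be recognisable from the image, which limits the benefit without cancelling it. The report should still say that masked change cannot be attributed to sonothrombolysis as distinct from PPCI or natural recovery.

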	 Complete (>50%) ST-segment resolution at 30 minutes post PCI as assessed by the worst lead on electrocardiogram (ECG core lab). Left ventricular ejection fraction (LVEF) by echocardiography (ECHO) (Simpson method) assessed on day 1 (pre and post reperfusion), day 3±2 (discharge) and 90±2 days after infarction. Wall motion score index (WMSI) by ECHO assessed on day 1 (pre and post reperfusion), day 3±2 (discharge) and 90±2 days after infarction. Microvascular perfusion score index (MPSI) by ECHO assessed on day 1 (pre and post reperfusion), day 3±2 (discharge) and 90±2 days after infarction.
Treatment	Sonothrombolysis: Echocardiographic imaging with intermittent diagnostic high mechanical index (MI) using a commercially available echocardiography scanner (Epiq,Philips Healthcare) to the myocardium during an intravenous 5% Definity infusion (Lantheus Medical) over a maximum 30 minute treatment period (started prior to PCI)

Statistical Considerations	Efficacy Analysis : This is an observational study to reproduce findings of a previous study which showed angiographic spontaneous reperfusion rates of 80% with sonothrombolysis prior to PCI (i.e. pre PCI TIMI 2-3 flow). If we can demonstrate a patency rate > 60%, a multicenter study will be arranged.
Sample Size	15 patients
Duration of Follow-Up	Minimum of 90 +/- 7 days

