Multiple mechanisms to reduce infarct size have been undertaken with limited success and inconsistent results(21). While transthoracic high mechanical index (MI) impulses from a diagnostic ultrasound (DUS) transducer have been utilized to diagnose microvascular obstruction and detect myocardial perfusion during a continuous microbubble infusion(22-26), the microbubble cavitation induced by these high MI impulses(27) creates shear forces that are capable of dissolving epicardial and microvascular thrombi in animal models of acute STEMI (28-30). These same high MI impulses, when applied to the microvasculature, also induce nitric oxide release (31), which may further augment microvascular flow. Termed sonothrombolysis, these effects have been demonstrated and verified in animal models, however the utility of DUS in humans has not been well studied during the contemporary management of STEMI, where emergent reperfusion (primary percutaneous coronary intervention [PPCI] or fibrinolysis) is routinely employed with such rapidity that only brief applications of ultrasound may be possible prior to interventional therapies. Recently in a small PPCI STEMI randomized trial (N=20 treated with sonothrobolysis), high MI with DUS (continuous microbubble infusion) (sonothrombolysis) was associated with improved patency rates of the infarct vessel prior to PCI. Specifically, the infarct related artery was found to be open in 80% with sonothrombolys is compared to patients with standard of care prior to PCI (~20%). If these results can be reproduced with another ultrasound system, a large clinical trial may be warranted (32). No serious adverse events were reported in this study and in a small previous study involving five patients (33). However, in another study vasoconstriction in the culprit coronary artery was observed in three out of six patients during coronary angiography (34). In this study the pulse duration of the ultrasound scanner was prolonged in order to expose the intracoronary thrombus and the ultrasound contrast to a higher power. One patient withdrew from the study and was lost during follow up (but still alive according to the Dutch national registry), the other two patients had no long term side effects. The authors stress the higher ultrasound power used in this trial (20 µs instead of 5 µs which is transmitted in diagnostic ultrasound) and explain the findings by a "summative effect of

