Sonothrombolysis in Patients with an ST-segment Elevation Myocardial Infarction Protocol #ST2017-Pro00067953 Version (3): 13-Feb-2017 myocardial ischemia, reperfusion, damage and long-pulse-duration sonoporation on endothelial damage, all leading to calcium overload. It was concluded that new trials should proceed with short (5 μ s) pulse duration. Therefore we will use the pulse duration of 5 μ s which is clinically used for diagnostic ultrasound in the proposed pilot study.

The purpose of this study was to examine what effect adding emergent DUS guided high MI impulses (sonothrrombolysis), applied both before PPCI during an intravenous commercially available microbubble infusion (5% Definity, Lantheus Medical Imaging, Inc., North Billerica, Massachusetts), have on spontaneous reperfusion (i.e. pre PCI coronary artery patency rates), microvascular obstruction, left ventricular function and infarct size in patients presenting with their first STEMI. Accordingly, given the potential impact of utilizing this practical application for attenuating reperfusion injury, we propose a prospective, single center, single-arm study of pre-procedural sonothrombolysis as an adjuvant to contemporary therapy for ST-segment elevation myocardial infarction receiving PPCI.

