4.2. Secondary Objective

To determine whether the use of sonothrombolys is along with standard therapy in patients with STEMI undergoing reperfusion therapy (primary PCI) is resulting in better microvascular function than what is reported for standard therapy alone.

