5.2. Intervention (sonothrombolysis)

Patients will immediately receive an intravenous infusion of commercially available ultrasound contrast agent (5% Definity, Lantheus Medical Imaging, Inc., North Billerica, Massachusetts)

1.3 mL diluted in 50 ml saline and infused running at 2 to 5 ml/min. After starting the infusion, myocardial contrast echocardiography will be performed using a commercially available echocardiography scanner (Epiq, Philips) with a diagnostic ultrasound transducer (X5-1) and a preset for myocardial perfusion imaging. 4-, 2- und 3-chamber views will be recorded to document the size of the perfusion defect according to method published by Porter et al (27). The focus will be set at the mitral valve level for all studies. Loops of 15 cardiac cycles will be recorded using low mechanical index (MI) ultrasound with a 'flash' delivered after the second cardiac cycle of the loop. The flash is a short impulse of high MI ultrasound* which is transmitted to destroy the ultrasound contrast in the myocardium and then to assess the replenishment of myocardial contrast. These recordings will also be used to assess regional wall motion as well as the LV volumes and ejection fraction.

* Mechanical index (MI) is the unit to measure the ultrasound energy transmitted by the ultrasound transducer. High MI (>0.8) ultrasound imaging is the standard for echocardiographic imaging without contrast agents. In contrast echocardiography, however, high MI leads to destruction of the microbubbles in the contrast agent. Therefore contrast imaging has to be performed with very low MI (<0.2), fortunately there are very sensitive postprocessing tools that can still detect the specific signals from contrast agent at very low MI. In myocardial perfusion imaging, high MI ultrasound is applied only briefly to clear the myocardium from the contrast agent and to assess the time it takes for the blood from the aorta to reach the microvessels. In diagnostic imaging this is performed several times in multiple imaging planes in order to detect myocardial thickening and to assess myocardial perfusion. In this pilot trial we are using the same techniques. The ultrasound scanning time will be in the range of that of echocardiographic imaging in clinical practice. The total

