day 1	12-lead electrocardiogram-immediately prior to PPCI	in cath lab	
Reperfusion (PPCI)			
day 1	Sonothrombolys is B	start immediately after reperfusion to complete a total of 30 min same method as before reperfusion	
day 1	12-lead electrocardiogram-30 min post PCI	in CCU	
day 1	Diagnostic ultrasound – post intervention	Myocardial Contrast Echo LV ejection fraction WMSI Global longitudinal strain	
day3/discharge	Diagnostic ultrasound	Myocardial Contrast Echo LV ejection fraction WMSI Global longitudinal strain	
day3/discharge	12-lead electrocardiogram-discharge	in CCU/Ward	
3 months	Diagnostic ultrasound	Myocardial Contrast Echo LV ejection fraction WMSI Longitudinal strain	

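### Session B after PCI has no patient-level rule to withhold or stop it when culprit-artery vasospasm has just been seen

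*Combined protocol and SAP*

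**What the plan says.** Table 1 in Section 5.2 gives the day-1 order: baseline contrast echo, session A, ECG, PPCI, session B, ECG at 30 minutes after PCI, and a post-intervention contrast echo. Session B is to "start immediately after reperfusion to complete a total of 30 min same method as before reperfusion". The Treatment row of the Synopsis sets the overall limit: the infusion runs "over a maximum 30 minute treatment period (started prior to PCI"). Session B therefore applies to every treated patient who has had less than 30 minutes by the time of PCI.

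Section 7.3 lists three safety outcomes. The second is "Vasospasm in culprit coronary artery"; the others are allergic reaction to Definity and adverse events. Section 2.0 explains the interest in vasospasm: in a study with longer pulses, "vasoconstriction in the culprit coronary artery was observed in three out of six patients during coronary angiography". The response is in the same section. "It was concluded that new trials should proceed with short" pulses, and this study accordingly uses 5 µs instead of 20 µs. Section 5.2 adds that total Definity will "not exceed the maximum dose which is approved for clinical use".

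Session B has a purpose. The secondary objective (Section 4.2) asks whether treatment "is resulting in better microvascular function than what is reported for standard therapy alone", and ultrasound after reperfusion may serve that aim.

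**The concern.** The diagnostic angiogram and PCI come between sessions A and B, so culprit-artery spasm can be visible just before B is due. The table then gives an affirmative instruction to repeat the same method, limited only by total time. Followed as written, a patient with spasm receives more of the treatment under study immediately after reperfusion. That exposure cannot help the primary outcome (Section 7.1) or the Synopsis criterion of patency above 60%, since both are read before PCI.

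A smaller matter follows from the same sequence. Everything Table 1 schedules after session B is ECG or ultrasound. These may show ischaemia indirectly, but they do not show spasm directly. A report of no vasospasm in 15 patients could be taken to cover all the treatment given, when scheduled angiographic assessment would have covered only the time before B.

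**Working it through.** The plan states no figure on this point, so there is nothing to reproduce. The check is a search for a rule, followed by arithmetic for scale.

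**1. Is there a rule anywhere?**

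| Place | What it provides | Does it tell staff what to do about B after spasm? |
|---|---|---|
| Section 2.0 | 5 µs pulses | No. It lowers expected risk in A and B alike |
| Section 5.2 | Dose cap; 5 to 15 s between impulses, set by contrast replenishment | No. Not tied to a clinical event |
| Synopsis, Treatment | 30-minute maximum | No. Time only |
| Section 6.2 | Excludes suspected hypersensitivity | No. Applies at entry; spasm not listed |
| Section 12 | No treatment if echo staff arrive late | No. Logistic |
| Section 10 | Monthly investigator meetings | No. Too slow for one procedure |
| Appendix | SAE form records action taken with the drug | No. Records an action, sets none |

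**2. How often might the rule be needed?** The rate *p* of culprit spasm by the end of PCI at 5 µs is not given, so it is assumed over a range. With all 15 patients treated, P(at least one) = 1 − (1 − p)^15:

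- p = 1%: 1 − 0.99^15 = 14%
- p = 2%: 1 − 0.98^15 = 26%
- p = 5%: 1 − 0.95^15 = 54%
- p = 10%: 1 − 0.90^15 = 79%

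The 3 of 6 at 20 µs has an exact (Clopper-Pearson) 95% interval of 12% to 88%. It is not carried over to 5 µs.

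**3. How much treatment can fall in session B?** The length A of session A is not given. For a full 30 minutes the share after the last scheduled angiographic view is (30 − A)/30. At one impulse every 5 to 15 s, B contains (30 − A) × 60/15 to (30 − A) × 60/5 impulses.

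Contrast supply may shorten B. The preparation is "1.3 mL diluted in 50 ml saline and infused running at 2 to 5 ml/min", so one preparation lasts 50/5 = 10 to 50/2 = 25 minutes. Thirty minutes needs 30 × 2 = 60 ml to 30 × 5 = 150 ml. If only one preparation is used, the share is at most (25 − A)/25, before allowing for the baseline study.

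| Assumed A (min) | Share in B, full 30 min | Impulses in B, full 30 min | Share in B, one preparation (at most) |
|---|---|---|---|
| 10 | 67% | 80–240 | 60% |
| 15 | 50% | 60–180 | 40% |
| 20 | 33% | 40–120 | 20% |
| 25 | 17% | 20–60 | 0% |

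**4. What would a clean result cover?** With no spasm in 15 treated patients, the one-sided 95% upper bound is 1 − 0.05^(1/15) = 18.1%. It applies to the period before B. For B there is no scheduled angiographic reading, hence no such bound.

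**The case against.** The strongest reply is that safety was considered and that B inherits the precautions. The pulse length was chosen because of the vasoconstriction report, and using the same method carries that choice into B. Section 2.0 also reports no serious adverse events in the earlier randomised trial (20 treated) or in a five-patient study. All of this stands. A reader might infer from Table 1 that session B has no safety control; the documents do not support that. What is absent is an instruction for the individual patient who has spasm despite the precautions. Nor does the reassuring evidence make such a patient implausible. It concerns serious events, not spasm, and even if it were read as no spasm in 20, the one-sided 95% upper bound would be 1 − 0.05^(1/20) = 13.9%.

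A reader might also infer that such a patient is re-exposed to the known cause of the spasm. That goes too far. Section 2.0 reports an attribution to a combination of ischaemia, reperfusion, damage and long pulses, and long pulses are not used here. In a single-arm study, spasm at angiography or during PCI cannot be assumed to come from session A; a catheter or wire may explain it. A rule that cancelled B for any spasm would therefore be too blunt.

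Operators would probably withhold B on judgement, and a suspected Definity reaction would very likely lead to stopping. This is a fair reason to rate the point low, and it reduces the Definity part to a clause. It does not remove the written instruction to proceed.

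Finally, Table 1 has no angiogram row at all; the diagnostic angiogram is known from Sections 7.1, 8.2.1 and 9. Its absence after B is therefore weak evidence of an oversight, and an unscheduled angiogram would still count. That part is only a reporting caveat.

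**Conclusion.** The point holds as a minor one: Table 1 directs staff to give session B to every patient with treatment time left, and no section says to withhold or stop it when culprit-artery vasospasm has just been seen. This rests on reading the documents, not on the arithmetic. The figures show scale only. The 14% to 79% depends on an assumed spasm rate of 1% to 10% and on all 15 patients being treated. The share of treatment in B ranges from 67% down to 0%, depending on the length of session A and the contrast supply. If session A uses the full 30 minutes, B does not occur.

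A reader might go on to conclude that session B should be dropped, that an angiogram after B is required, or that the main result is compromised. None of these follows. B fits the Synopsis and may serve the microvascular objective, another angiogram would add an invasive procedure, and the primary outcome and the 60% patency criterion are complete before B begins.

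**What to change.** Add to Table 1 and Section 5.2: session B is not started, or is stopped, if culprit-artery vasospasm is seen at angiography or PCI and is not explained by the catheter or wire or has not resolved with standard treatment, or if a Definity reaction is suspected; after a suspected reaction no further Definity is given. Under this wording B goes ahead only after spasm that is both explained by catheter or wire and resolved.

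Record on the CRF the minutes of session B given and the reason if it was withheld or shortened. When vasospasm is reported, state that scheduled angiographic assessment covers only the period before B.

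The cost is one sentence of treatment rule, one sentence of reporting and two CRF fields. Affected patients receive less than 30 minutes of treatment, which may reduce any microvascular effect in them. Those with a suspected reaction also lose later contrast-based WMSI and MPSI. The primary outcome and the 60% patency criterion do not change.
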